# Statistical Considerations

The objective of the statistical analysis is to evaluate agreement in sphere, cylinder, and axis measurements between LFR-260 and traditional refraction performed by a traditional phoropter. Specifically, the subjective manifest refraction measured by means of a traditional phoropter will serve as the reference control and is considered to be the gold standard for the purpose of this evaluation.

The accuracy of the acuity measurement obtained by the LFR-260 will be evaluated for both cases (uncorrected, corrected) measured with the conventional phoropter. It will be assessed comparing the LFR-260 acuity measurement to the conventional acuity measurement using a Snellen chart (scored to the letter), with similar analyses used for the refractive components.

For each measurement, the paired difference will be computed. Good clinical agreement is defined a priori as  $\leq \pm 0.5$  D for sphere and cylinder measurements and  $\leq \pm 10$  degrees for axis measurements for subjects with low astigmatism and  $\leq \pm 5$  degrees for axis measurements for subjects with low astigmatism.

The unit of analysis will be the individual eye. Overall device performance will be summarized as the number of and percentage of eyes meeting three of the good clinical agreement criteria listed above.

the mean of measurements will characterized.

A supporting analysis will evaluate the vector difference between investigational device measurements and the gold standard in terms of sphere and cylinder measurements. The vector differences is square root of (X1-Y1) + (X2-Y2) where the X1 and X2 are measurements of sphere and cylinder using the investigational devices and Y1 and Y2 are the same measurements using the gold standard.

Homogeneity of treatment effects across sites will be evaluated comparing site level differences between the investigational device and the gold standard separately for sphere, cylinder, and axis and also for the vector analysis of sphere and cylinder.

Similarly, differences between measurements from the investigational device and the gold standard device will be summarized by gender, age category, race, and ethnicity to investigate consistency or heterogeneity of the treatment effect across those subgroups, separately for sphere, cylinder, and axis and also for the vector analysis of sphere and cylinder.

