# 4.3 Control group

The control group is a traditional refraction performed by a phoropter. The results for both refractions will be recorded separating the components Sphere (S), Cylinder (C) and Axis (A). A calculation of the spherical equivalent will be performed at the end of the visit and both values will be recorded in the study documentation. The best corrected visual acuity for each measurement will be recorded.

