# 7.7 Other Planned Analyses

#### 7.7.1 Bland-Altman Agreement Analysis

Supporting analyses will evaluate the distribution of paired differences between LFR-260 and reference for the three dimensions (sphere, cylinder, and axis) using Bland-Altman agreement analysis. This will include determination of the standard deviation of paired differences, the 95% limits of agreement, and an evaluation of systematic bias. The Bland-Altman plot of paired differences versus the mean of measurements will be provided. The relationship between bias and the mean of measurements will characterized. The same analysis will be applied to the vector difference between LFR-260 measurements and the gold standard in terms of sphere and cylinder measurements. The vector differences is square root of (X1-Y1) + (X2-Y2) where the X1 and X2 are measurements of sphere and cylinder using the investigational devices and Y1 and Y2 are the same measurements using the gold standard.

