# 7.7.2 Poolability and Homogeneity of Treatment Effects

Homogeneity of treatment effects across sites will be evaluated by comparing differences between the LFR-260 and the gold standard separately for sphere, cylinder, and axis and also for the vector analysis of sphere and cylinder.

Similarly, differences between measurements from the investigational device and the gold standard device will be summarized by gender, age category, race, and ethnicity to investigate consistency or heterogeneity of the treatment effect across those subgroups, separately for sphere, cylinder, and axis and also for the vector analysis of sphere and cylinder.

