# 7.7.4 Reliability and Repeatability Analysis

Reliability of LFR-260 will be conducted in a subset of subjects for which measurements will be obtained twice in an office context. This analysis will be repeated in a remote context. Reliability will be evaluated using intraclass correlations for each of the continuous measurements, sphere, cylinder, and axis and for the vector measurement of sphere and cylinder.

For a subset of 33 subjects (66 eyes), the LFR-260 device will be measured again approximately 60 minutes after the initial assessment in order to measure the repeatability/accuracy of the device.

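### The supporting vector difference is built from sphere and cylinder power only, so axis disagreement contributes nothing to it

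*Combined protocol and SAP*

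**What the plan says.** The synopsis (Statistical Considerations) introduces the measure as supporting: "A supporting analysis will evaluate the vector difference between investigational device measurements and the gold standard". Section 7.7.1 applies Bland-Altman methods to it and defines it as √[(X1 − Y1) + (X2 − Y2)], "where the X1 and X2 are measurements of sphere and cylinder using the investigational devices", with Y1 and Y2 the same two measurements from the phoropter. The synopsis carries the same definition.

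The measure is then reused:

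- Section 7.7.2 assesses site and subgroup consistency separately for sphere, cylinder and axis, and "also for the vector analysis of sphere and cylinder".
- Section 7.7.4 plans intraclass correlations for sphere, cylinder and axis, and "for the vector measurement of sphere and cylinder".

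Section 4.3 has sphere, cylinder and axis recorded as separate components for both refractions, and section 4.4 has both eyes tested with both devices. The primary hypothesis (sections 2.5.1 and 7.4) requires agreement on sphere, cylinder and axis together, with an axis limit of 10 degrees in low astigmatism and 5 degrees in moderate to high astigmatism.

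**The concern.** In refraction, cylinder power and axis together describe one astigmatic correction. The optical effect of an axis error depends on how much cylinder is present. The protocol accepts this in its primary criterion, where the axis limit is tighter when astigmatism is greater. A combined measure in dioptres is the natural place for that dependence to appear, but the planned vector uses cylinder power without its direction.

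The separate axis analyses do not fill the gap. They are in degrees and give an axis error the same weight at any cylinder. The primary composite uses axis as pass or fail and gives no size in dioptres, and sections 7.7.2 and 7.7.4 do not plan to use it. If one site, or one repeat setting, had larger axis errors in eyes with substantial cylinder, the vector results there would not show it.

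**Working it through.** **Plan's own figures.** The documents give no value for the vector difference, so there is none to reproduce. The one nearby figure, 99% power in section 7.5, does reproduce. With 216 eyes treated as independent, one-sided alpha 0.05, a goal of 0.80 and a true rate of 0.90, the exact binomial test needs at least 183 successes, with type I error 0.046 and power 0.995. The vector measure does not enter that calculation.

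**Inputs.** The definition comes from section 7.7.1 and the synopsis. The largest eligible cylinder, 2.5 D, comes from section 3.4. The documents give no distribution of cylinder or of axis error, so the sizes below are shown across a range of assumed values.

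**Planned measure.** With equal sphere and equal cylinder, X1 − Y1 = 0 and X2 − Y2 = 0, so the measure is 0 for every axis difference. This is true of the formula as printed and with squared terms. The printed text has no squares. They may have been lost in reading the PDF, and nothing here depends on them.

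**Axis-inclusive comparison.** For each refraction take M = S + C/2, J0 = −(C/2)cos(2A), J45 = −(C/2)sin(2A), and distance √(dM² + dJ0² + dJ45²). With equal S and C, dM = 0 and dJ0² + dJ45² = (C/2)² × 4 sin²(dA). The distance is therefore |C| × |sin(dA)|.

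*Worked example.* Compare −2.00/−2.50 × 180 with −2.00/−2.50 × 90. M is −3.25 in both. J0 is +1.25 and −1.25, and J45 is 0 in both. The distance is 2.50 D, and the planned measure is 0.

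| Axis difference | Planned measure | C = 0.5 D | C = 1.0 D | C = 2.5 D |
|---|---|---|---|---|
| 5° | 0 | 0.04 D | 0.09 D | 0.22 D |
| 10° | 0 | 0.09 D | 0.17 D | 0.43 D |
| 45° | 0 | 0.35 D | 0.71 D | 1.77 D |
| 90° | 0 | 0.50 D | 1.00 D | 2.50 D |

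**Weighting.** A 20-degree error (sin 20° = 0.342) is 0.25 × 0.342 = 0.09 D at 0.25 D of cylinder and 2.50 × 0.342 = 0.86 D at 2.50 D. The analysis in degrees records 20 in both eyes.

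**Direction of change.** Let sphere differ by +0.5 D and cylinder by −0.5 D at the same axis. The planned measure, with squares, is √(0.25 + 0.25) = 0.71 D. On the power-vector scale, dM = 0.5 − 0.25 = 0.25 and the astigmatic change is 0.25, so the distance is √(0.0625 + 0.0625) = 0.35 D. Here the planned measure shows the larger disagreement.

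**The case against.** The best defence is that axis is well covered elsewhere and that the plan never claims the vector includes it. Each mention limits it to sphere and cylinder. Section 7.7.1 plans a Bland-Altman analysis of axis itself, and sections 7.7.2 and 7.7.4 place an axis analysis beside the vector. The synopsis gives overall performance to the three-criterion composite, and no success rule depends on the vector. All of this stands, and it limits the weight of the point.

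A reader might infer more than the documents support:

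- *That the study would count opposite axes as agreement.* It would not. An eye with equal powers and axes 90 degrees apart fails the axis limit, is a failure in the primary analysis, and appears in the separate axis results.
- *That this is the only planned summary combining components.* The primary composite combines all three, and section 4.3 plans a spherical equivalent.
- *That the measure always overstates agreement.* It omits the axis contribution, but it also scales power errors differently, and the last example in the working goes the other way.
- *That the effect is twice as large.* Residual cylinder, 2C × sin(axis difference), gives 0.44, 0.87, 3.54 and 5.00 D at 2.5 D of cylinder. Those figures are correct on their own scale but are double what the corrected vector would report.

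It can also be said that renaming the measure would cure the label. That is true, but it would leave the plan without a dioptric measure of axis disagreement.

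**Conclusion.** The point holds for the supporting vector measure and its reuse in sections 7.7.2 and 7.7.4: axis error contributes nothing to it, and no other planned continuous measure expresses that error in dioptres, weighted by cylinder. The omitted amount is C × sin(axis difference) when powers are equal. At the eligibility limit of 2.5 D it runs from 0.22 D at 5 degrees to 2.50 D at 90 degrees. At 0.5 D of cylinder it never exceeds 0.50 D.

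The large values are extremes. In an eye that just meets a 5-degree limit, the omission is at most 0.22 D. The typical effect cannot be stated without the distributions of cylinder and axis error, which the documents do not give. The correction should be made before analysis because it is cheap and improves three analysis sections. It is not a threat to the primary conclusion: the endpoint, exact test, sample size and 99% power do not depend on this measure.

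**What to change.** In the synopsis and sections 7.7.1, 7.7.2 and 7.7.4, replace the two-component vector as follows:

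1. For each eye and each device, compute M = S + C/2, J0 = −(C/2)cos(2A) and J45 = −(C/2)sin(2A). An eye with no cylinder has J0 = J45 = 0, so an undefined axis causes no difficulty.
2. Define the vector difference as √(dM² + dJ0² + dJ45²), with the squares written out.
3. In 7.7.1, report Bland-Altman results for dM, dJ0 and dJ45, with the vector difference as the overall size.
4. In 7.7.2, compare sites and subgroups on the same quantities. In 7.7.4, give intraclass correlations for M, J0 and J45.

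Keep the separate sphere, cylinder and axis analyses. If the two-component measure is kept as well, rename it and state that it excludes axis.

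The cost is some revised wording and a few lines of code. No new data are needed, and the primary analysis is untouched. The sponsor should expect reported vector agreement to move in either direction.

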# 7.7.2 Poolability and Homogeneity of Treatment Effects

Homogeneity of treatment effects across sites will be evaluated by comparing differences between the LFR-260 and the gold standard separately for sphere, cylinder, and axis and also for the vector analysis of sphere and cylinder.

Similarly, differences between measurements from the investigational device and the gold standard device will be summarized by gender, age category, race, and ethnicity to investigate consistency or heterogeneity of the treatment effect across those subgroups, separately for sphere, cylinder, and axis and also for the vector analysis of sphere and cylinder.

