# 3.0 Subject Selection

# 3.1 Number of Sites / Investigators

Investigators responsible for the conduct of this study in compliance with this protocol will be qualified ECPs (licensed optometrist or ophthalmologist) who are skilled in refraction testing via a traditional phoropter. Two (2) sites at 3 locations (one site has multiple satellite locations) in the United States will be selected for participation in this study. Each location will have 2 ECPs available for testing/evaluation for a total of 6 different ECPs for the study.

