#### 4.8 Randomization

The randomization will be performed between the LFR-260 and the traditional phoropter within site to account for the first system used. Randomization will be carried out according to the blocks procedure to avoid order imbalance of first device used in the trial.

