# 2. Reproducibility Testing

In a separate subset of 33 patients (11 per location), LFR-260 testing will be reproduced by two separate ECP operators at each location for a total of 6 ECPs.

If the patient is randomized to Group I, the steps listed below will be completed at the beginning of the patient visit. If the patient is randomized to Group II, the steps listed below will be completed after the eye exam with use of the traditional phoropter.

- 1. ECP #1 will complete Refraction with LFR-260.
  - a. Best Corrected Visual Acuity will be measured.
- 2. ECP #1 will leave the room, and ECP #2 will complete Refraction with LFR-260.
  - a. Best Corrected Visual Acuity will be measured.

3. Conclusion of Study: Study coordinator will complete the Study Exit Form, which will indicate the conclusion of subject participation in this study.

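### The supporting homogeneity check compares 2 sites although the study runs at 3 locations with 6 ECPs, so a shift at one location of the multi-location site is diluted or cancelled

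*Combined protocol and SAP*

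**What the plan says.** Section 3.1 uses site and location as different words: "Two (2) sites at 3 locations (one site has multiple satellite locations) in the United States will be selected". It adds: "Each location will have 2 ECPs available for testing/evaluation for a total of 6 different ECPs for the study". Three locations over two sites can only split two and one.

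The homogeneity check is by site in both places where it appears. Section 7.7.2 says "Homogeneity of treatment effects across sites will be evaluated by comparing differences between the LFR-260 and the gold standard", separately for sphere, cylinder, axis and the sphere-cylinder vector. The synopsis (Statistical Considerations) says "Homogeneity of treatment effects across sites will be evaluated comparing site level differences between the investigational device and the gold standard". Neither names a test, a significance level or a rule for pooling.

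The only other groupings of the paired difference are demographic. In section 7.7.2 the differences "will be summarized by gender, age category, race, and ethnicity". Section 4.8 also works at site level: "The randomization will be performed between the LFR-260 and the traditional phoropter within site to account for the first system used".

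The nearest examiner check is the reproducibility subset in section 4.9.2 (33 subjects, 11 per location), where "LFR-260 testing will be reproduced by two separate ECP operators at each location for a total of 6 ECPs". The synopsis plans intraclass correlations for it.

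**The concern.** Subjective refraction depends on who performs it and where. Three features of the plan make location a plausible source of difference:

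- Each location has its own pair of ECPs (section 3.1).
- The synopsis allows any legally marketed 510(k)-exempt phoropter as comparator, so the reference instrument may differ between locations.
- Section 4.4 lets the test distance be adjusted to the dimensions of the office.

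The protocol already treats location as a unit when it allocates the precision, offsite and remote subsets (11, 11, 7 and 7 subjects per location).

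Grouping by site merges two locations and four ECPs before any comparison is made, and leaves a single contrast with 1 degree of freedom. Grouping by location would have 2 degrees of freedom, and by ECP 5. At stake is whether the report would show that one location behaves differently from the others.

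**Working it through.** **The plan's own figure.** Section 7.5 states 99% power for 216 eyes, true agreement 0.90, goal 0.80, one-sided alpha 0.05. The smallest count r with P(X ≥ r | 216, 0.80) ≤ 0.05 is r = 183 (183/216 = 84.7%). The exact alpha is 0.0461 and the power at 0.90 is 0.9946. The stated figure reproduces and does not depend on how homogeneity is grouped.

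**Inputs for the illustration.** From the documents: 216 eyes, 108 subjects, 2 sites, 3 locations. Assumed, because the documents give no values:

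- equal enrolment, so 216/3 = 72 eyes per location;
- design effect 1.5 for two eyes per subject;
- SD of the paired difference 0.30 to 0.50 D;
- two-sided 0.05.

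**Dilution.** Let the two locations of the multi-location site have mean shifts a and b, and the other site none. The site contrast is (a + b)/2. With a = 0.25 D and b = 0 it is 0.125 D, half the true shift. With a = −b it is 0.

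**Power by site** (normal test). SE = SD × √(1.5 × (1/72 + 1/144)) = SD × 0.1768. At SD 0.30 D, SE = 0.0530 D, so a 0.25 D shift at one such location gives z = 0.125/0.0530 = 2.36 and power 0.65.

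**Power by location** (noncentral chi-square, 2 df). Noncentrality = Σ(shift − mean shift)² / (1.5 × SD²/72). For shifts of 0.25, 0, 0 the sum of squares is 0.25² × 2/3 = 0.04167. At SD 0.30 D the divisor is 0.001875, so the noncentrality is 22.2 and the power 0.99.

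| Shift at one location of the multi-location site | SD (D) | Power by site | Power by location |
|---|---|---|---|
| 0.25 D | 0.30 | 0.65 | 0.99 |
| 0.25 D | 0.40 | 0.42 | 0.90 |
| 0.25 D | 0.50 | 0.29 | 0.72 |
| 0.125 D | 0.30 | 0.22 | 0.55 |
| 0.125 D | 0.40 | 0.14 | 0.33 |
| 0.125 D | 0.50 | 0.11 | 0.23 |

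Opposite shifts of 0.25 D at the two locations are detected by site only at the 5% false-positive rate, against more than 0.99 by location at each of these SDs.

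**The reverse case.** If the shift is at the single-location site, the site contrast carries it in full. At SD 0.30 D the power is then 0.997 by site against 0.992 by location for 0.25 D, and 0.65 against 0.55 for 0.125 D.

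**A low location behind a pass.** Take true agreement of 0.95 and 0.75 at the two locations of one site and 0.95 at the other site. The two-location site shows (0.95 + 0.75)/2 = 0.85 and the pooled rate is 2.65/3 = 0.883. Adding three binomial counts of 72 eyes gives P(total ≥ 183) = 0.96 with eyes independent. As a rough allowance for paired eyes, the expected count is 72 × 2.65 = 190.8 and the binomial variance is 72 × (2 × 0.95 × 0.05 + 0.75 × 0.25) = 20.34. Inflating the variance by 1.5 gives z = (190.8 − 182.5)/√30.51 = 1.50, a probability of about 0.93.

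**The case against.** The strongest reply is that this analysis decides nothing. Section 7.6 sets the decision by the exact binomial lower bound alone, and 7.7.2 sits under other planned analyses. A reader might infer that the pooled primary result rests on the homogeneity check, or that the plan could formally declare unlike data poolable. The documents support neither, because 7.7.2 contains no test and no pooling rule. The powers above therefore belong to tests supplied here for illustration.

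A reader might also infer that opposite shifts would pass through the study unseen. They cancel in a site mean, but the primary endpoint counts eyes within ±0.5 D, so a shift in either direction lowers it. For sphere alone, with normal differences and SD 0.30 D, agreement is 90.4% with no shift and 79.1% with a 0.25 D shift. Two shifted locations give (2 × 79.1 + 90.4)/3 = 82.9% pooled, and the primary would pass with probability only about 0.27 (eyes independent), before cylinder and axis are counted. The Bland-Altman limits in 7.7.1 would widen too. The one-location shift is the harder case: sphere alone, the primary still passes with probability about 0.83.

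The reproducibility subset is a real safeguard for examiner differences in LFR-260 readings, so those are not unchecked. It compares LFR-260 with LFR-260, between two ECPs at the same location. It cannot show a difference between locations shared by both ECPs, or an ECP effect on the device-phoropter difference.

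Site also matches the randomization stratum, and site grouping is better when the shift is at the single-location site. Both points stand, and they are reasons to keep the site comparison alongside the location one. If the sponsor means location by site in 7.7.2, the text should say so, because section 3.1 uses the words differently.

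**Conclusion.** The concern holds as a limited point about a supporting analysis. The grouping in 7.7.2 and the synopsis is coarser than the structure in section 3.1, and nothing else planned examines the LFR-260 minus phoropter difference by location or ECP. ECP effects are pooled inside the single-location site as well.

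The halving and the cancellation follow from the grouping (the exact half assumes equal enrolment at the two locations). The sizes in the table rest on the assumed enrolment, SD, design effect and tests. Over the SD range shown, location grouping has at least twice the power by site for a shift inside the multi-location site, except for 0.25 D at SD 0.30 D (0.99 against 0.65). It does not win everywhere, as the reverse case shows.

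The practical consequence is one of reporting: a primary pass could coexist with a location below the 0.80 goal, and no planned table would reveal it. The change is desirable but not essential to the validity of the primary test.

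**What to change.** In section 7.7.2 and the synopsis:

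- Evaluate homogeneity of the paired difference across the 3 locations (2 degrees of freedom), with errors clustered by subject.
- Keep the 2-site comparison as a secondary grouping. This covers the modest loss of power when the shift is at the single-location site.
- Report the proportion of eyes meeting the agreement criteria by location.
- Tabulate mean difference and agreement proportion by ECP, descriptively. An equal split would give 216/6 = 36 eyes (18 subjects) per ECP, but section 3.1 says only that two ECPs are available at each location, so actual numbers may be uneven.
- Require location and ECP to be recorded for each refraction. The protocol does not state that they are, and section 4.9.1 does not say that one ECP performs both refractions.

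The cost is a wording change in two places, one more table and, if not already captured, two fields on the case report form. No extra subjects or visits are needed, and the primary analysis does not change.
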